#### Sample size

The expected median [TIMP-2]\*[IGFBP7] level in the control group is median control=0.84 (Q1=0.35, Q3=1.57) and in the AT-II group median AT-II=0.58 (Q1=0.26, Q3=1.20), based on Meersch et al., Intensive Care Med 2017. A total number of 64 patients will be recruited and a number of 32 patients will be randomized to each of the two treatment arms. With an expected 5% dropout rate, up to 2 patients per treatment arm will be non-evaluable. With a number of n=30 evaluable patients per treatment arm, the location shift between the distributions of the biomarker [TIMP-2]\*[IGFBP7] in the AT-II and the control group can be estimated with an expected precision  $\pm 0.285\text{ng/ml}^2/1000$  (half-width of the 90% confidence interval).

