# 1 General Information

## 1.1 Synopsis

Title:	Biomarker-guided implementation of angiotensin-II (AT-II) to reduce the occurrence of kidney damage after cardiac surgery
Short Title:	Aided-Trial
Sponsor's Study Code:	WWU20_0016
EudraCT-No.:	2021-003088-87
Sponsor:	Westfälische Wilhelms-Universität Münster
Investigator:	Univ.-[name]. med. [name]
Indication:	Cardiac surgical patients at high risk for AKI
Study Design:	Single-centre clinical Trial Two-arm, randomised, blinded, controlled, parallel-group trial
Investigational Medicinal Product:	Test product: Angiotensin II acetat (Giapreza 2,5 mg/ml) Reference therapy: Placebo (0.9 % NaCl)
Therapy	
After identifying cardiac surgery patients at high risk for AKI by renin levels (<math>\Delta</math>-renin (difference between post- and pre-operation) <math>\geq</math> 3.7 <math>\mu</math>U/ml 4h after CPB) who require vasopressors, patients will be randomly allocated to the control or intervention group.
 
Experimental intervention: Angiotensin II will be added to the first-line vasopressor (norepinephrine) and the angiotensin II dose and norepinephrine will be adjusted so that the mean arterial pressure is above 65 mmHg and the first-line vasopressor (norepinephrine) can completely be weaned..
 
Control intervention: The control substance (0.9% NaCl) will be added to the first-line vasopressor (norepinephrine) and the dose of the control substance and norepinephrine will be adjusted so that the mean arterial pressure is above 65 mmHg.
 
The treatment with study medication will be performed for 12 hours. If the patient requires a vasopressor after the intervention period, the first-line vasopressor (norepinephrine) is administered..

Objectives:	
The primary objective of this trial is to investigate the efficacy of AT-II vs. standard of care on the biomarkers [TIMP-2]*[IGFBP7] in high-risk patients undergoing cardiac surgery.
 
HYPOTHESIS: Superiority of AT-II in cardiac surgery patient with a hyperreninemia and vasopressor use compared to standard of care with respect to kidney damage (personalized approach).

Endpoints:	
Primary Endpoint:
 

• kidney damage after cardiac surgery identified by the difference between [TIMP-2]*[IGFBP7] levels 12h after

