	
randomization and [TIMP-2]*[IGFBP7] levels at randomization
 
Secondary Endpoints:
 
 
• occurrence of AKI within 72h after cardiac surgery (according to the KDIGO criteria)
 
• occurrence of moderate and severe AKI within 72h after cardiac surgery (according to the KDIGO stage 2 and 3)
 
• amount of volume application
 
• transient (<72h) and persistent (<72h) AKI
 
• fluid status
 
• dose and duration of vasopressor use
 
• creatinine clearance on day one after cardiac surgery
 
• free-days through day 28 of vasoactive medications and mechanical ventilation
 
• renal recovery at day 90 (renal recovery is defined as serum creatinine levels < 0.5 mg/dl higher than baseline serum creatinine (creatinine level before surgery)
 
• 30-day, 60-day and 90-day mortality
 
• length of ICU stay
 
• length of hospital stay
 
• use and duration of renal replacement therapy within hospital stay
 
• use of RRT at days 30, 60, 90
 
• MAKE90 (major adverse kidney events consisting of mortality, dialysis dependency, persistent renal dysfunction (defined as serum creatinine <math>\geq</math> 2x compared to baseline value) at day 90
 
• Effect of ACEi/ARBs use on the AT II effect
 
• Correlation between the severity of hyperreninemia and the AT II effect
 
 
Other variables:
 
 
• Surveillance of vital parameters on ICU
 
• Safety laboratory parameters
 
• Occurrence of thromboembolism
 
• Adverse events
 
 
Add-on study:
 
 
• determination of further biomarkers (e.g. KIM-1, chitinase, NGAL, hyaluronic acid) and anti- and pro-inflammatory mediators (IL-6, IL-10...)
 

Planned Number of Study Centers:	1

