Number of Patients/ Sample size:	Expected [TIMP-2]*[IGFBP7] level in the control group: median=0.84, Q1=0.35, Q3=1.57 and in the AT-II group: median=0.58, Q1=0.26, Q3=1.20 (based on Meersch et al., Intensive Care Med 2017). A total number of 64 patients will be recruited and a number of 32 patients will be randomized to each of the two treatment arms. With an expected 5% dropout rate, up to 2 patients per treatment arm will be non-evaluable. With a number of n=30 evaluable patients per treatment arm, the location shift between the distributions of the biomarker [TIMP-2]*[IGFBP7] in the AT-II and the control group can be

	estimated with an expected precision $\pm 0.35\text{ng/ml}^2/1000$ (half-width of the 95% confidence interval).
Inclusion Criteria:	
Inclusion criteria for registration
 
 
1. Adult patients scheduled for cardiac surgery with cardiopulmonary bypass (CPB),
 
2. 18 years of age or older,
 
3. cardiac index <math>> 2.1 \text{ l/min per square meter}</math>,
 
4. Written informed consent.
 
 
Inclusion criteria for randomization
 
Registered patients will be randomized only if
 
 
1. <math>\Delta</math>-renin (difference between post- and pre-operation) <math>\geq 3.7 \mu\text{U/ml}</math> 4h after CPB.
 
2. postoperative hypotension requiring vasopressors
 

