## 3.2 Endpoints

### 3.2.1 Primary Endpoint

The primary study endpoint is

- **Difference between [TIMP-2]\*[IGFBP7] levels 12h after randomization and [TIMP-2]\*[IGFBP7] levels at randomization.**

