## 10 Assessment of Efficacy and Safety

### 10.1 Assessment of Efficacy

Kidney damage after cardiac surgery identified by the difference between [TIMP-2]\*[IGFBP7] levels 12h after start of study medication and [TIMP-2]\*[IGFBP7] levels at randomization

To understand the mechanisms of illness and recovery and how AT-II affects them, markers of inflammation, oxidative stress, cellular hypoxia, and coagulation will be measured. Furthermore, leukocyte functions will be investigated.

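### The half-widths that justify n=64 are built from biomarker levels, while the primary endpoint is the change from randomisation to 12 h; no precision is shown for that change

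*Protocol*

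**What the plan says.** **Endpoint.** The synopsis (Section 1.1, Endpoints) describes the primary endpoint as "kidney damage after cardiac surgery identified by the difference between [TIMP-2]*[IGFBP7] levels 12h after" "randomization and [TIMP-2]*[IGFBP7] levels at randomization". Section 3.2.1 also takes the difference of "levels 12h after randomization and" those at randomisation. Section 10.1 again uses a difference from the value at randomisation ("Kidney damage after cardiac surgery identified by the difference between" the two measurements), counting the 12 hours from the start of study medication. All three describe a change.

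**Sample size.** Section 12 gives the planning values as a "level in the control group is median control=0.84 (Q1=0.35, Q3=1.57) and in the AT-II group median AT-II=0.58", with AT-II quartiles 0.26 and 1.20. The synopsis has the same numbers: "level in the control group: median=0.84, Q1=0.35, Q3=1.57 and in the AT-II group: median=0.58, Q1=0.26, Q3=1.20". Both plan 32 patients per arm, 30 of them evaluable. Section 12 then states an expected precision of ±0.285, called the "half-width of the 90% confidence interval"; the synopsis states ±0.35, called the "half-width of the 95% confidence interval". Neither place says which time point the planning levels refer to.

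**Analysis.** In the synopsis and in Section 12 the primary analysis is a non-parametric confidence interval for the location shift between the arms' biomarker distributions. Neither text says whether the variable is the level or the change.

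**The concern.** The precision of a level at one time and the precision of a change from baseline are different quantities. The second depends also on the spread at randomisation and on how strongly the two measurements in one patient are correlated. With high correlation, subtracting the baseline removes variation and narrows the interval. With low correlation it adds variation and widens it. The protocol supplies neither input.

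That the planning values are levels and not changes is inferred from two things: the protocol calls them levels, and all the quartiles are positive.

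Expected precision is the only argument the protocol offers for 64 patients; no power is claimed. If that precision belongs to another quantity, a reader cannot tell what 64 patients deliver for the declared endpoint.

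**Working it through.** **Inputs from the protocol (Sections 1.1 and 12).** Control: Q1 0.35, median 0.84, Q3 1.57. AT-II: Q1 0.26, median 0.58, Q3 1.20. Evaluable patients: 30 per arm. Stated half-widths: 0.285 (90%) and 0.35 (95%).

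**Step 1: interval.** For a rank-based (Hodges-Lehmann) interval with n per arm, sort the n² pairwise differences and take c = floor(n²/2 − z·√(n²(2n+1)/12)). The half-width is half the distance between the c-th smallest and the c-th largest difference. With n = 30, √(900·61/12) = 67.64. So c = floor(450 − 1.645·67.64) = 338 for 90%, and c = floor(450 − 1.960·67.64) = 317 for 95%. The expected half-width is the mean over 6,000 simulated trials.

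**Step 2: reproduce the stated figures from levels alone.** Fit a lognormal to the quartiles: μ = (ln Q1 + ln Q3)/2 and σ = (ln Q3 − ln Q1)/(2·0.6745).

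- Control: μ = (−1.050 + 0.451)/2 = −0.299; σ = 1.501/1.349 = 1.113. Implied median 0.74 (stated 0.84).
- AT-II: μ = (−1.347 + 0.182)/2 = −0.582; σ = 1.529/1.349 = 1.134. Implied median 0.56 (stated 0.58).

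| Distribution of the level | 90% | 95% |
|---|---|---|
| Stated in the protocol | 0.285 | 0.35 |
| Lognormal fitted to Q1 and Q3 | 0.289 | 0.354 |
| Lognormal, least squares on all three quantiles | 0.286 | 0.349 |
| Gamma fitted to the quartiles | 0.303 | 0.367 |
| Split lognormal matching all three quantiles | 0.304 | 0.369 |
| Lognormal centred on the stated medians | 0.321 | 0.392 |

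Both stated figures are recovered closely with no baseline term. This is consistent with a calculation on levels but does not prove one: the two closest fits miss the stated control median (0.74 and 0.79 against 0.84), and the other fits are wider.

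**Step 3: the change.** The protocol gives no baseline data, so these are assumptions. The 12-hour values follow the Step 2 lognormals. The value at randomisation follows the control distribution times a factor. The logs are bivariate normal with correlation r, the same in both arms. There are 30 patients per arm. Cells show 90% / 95% half-widths.

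| r | Factor 1 | Factor 0.5 | Factor 0.3 |
|---|---|---|---|
| 0.3 | 0.505 / 0.614 | 0.374 / 0.454 | 0.325 / 0.396 |
| 0.4 | 0.466 / 0.566 | 0.347 / 0.422 | 0.306 / 0.372 |
| 0.5 | 0.424 / 0.516 | 0.318 / 0.387 | 0.286 / 0.348 |
| 0.6 | 0.379 / 0.461 | 0.288 / 0.350 | 0.264 / 0.323 |
| 0.7 | 0.328 / 0.400 | 0.254 / 0.309 | 0.242 / 0.296 |
| 0.8 | 0.270 / 0.328 | 0.216 / 0.263 | 0.220 / 0.269 |
| 0.9 | 0.196 / 0.239 | 0.172 / 0.210 | 0.201 / 0.246 |

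The 95% figure of 0.35 is met at r of about 0.77 for factor 1 (interpolating: 0.7 + 0.1·(0.400 − 0.350)/(0.400 − 0.328)), about 0.6 for factor 0.5, and about 0.5 for factor 0.3. Below those correlations the interval is wider than stated; above them it is narrower.

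**Step 4: in patients.** By square-root-n scaling, the number per arm for a 95% half-width of 0.35 is 30·(half-width/0.35)². The extremes of the table give 30·(0.614/0.35)² ≈ 92 and 30·(0.210/0.35)² ≈ 11. These illustrate the dependence on the missing inputs; they are not proposed sample sizes.

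**The case against.** The strongest reply has four parts.

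1. *The derivation is not shown.* The protocol does not say how the half-widths were obtained, and picking the fit that matches proves nothing. That stands, so the conclusion is limited to the figures not being shown to apply to the change. It rests on the text, which offers levels as the only input, and not on the reconstruction.

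2. *The sample-size text matches the analysis text.* Both speak of the distributions of the biomarker, and the exact analysis variable may be fixed in a statistical analysis plan. The shared looseness is real, and it is a reason to name the variable. It does not rescue the figures: the protocol itself defines the endpoint as a change and itself justifies the sample size.

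3. *The range for the change is assumption.* Correct. The grid is not weighted by plausibility, and baselines larger than the control values are left out. At factor 1.5 the 95% half-width runs from 0.78 (r = 0.3) to 0.34 (r = 0.9). Counting wider and narrower settings therefore has no evidential weight.

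4. *Little depends on it.* Section 4 calls the study a feasibility trial, no decision rule uses the half-width, and the observed interval will show the precision achieved. This limits the consequence. But the same section makes a follow-up trial depend on showing that kidney damage is mitigated, so the expected precision for this endpoint deserves a correct statement.

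The difference between 90% and 95% intervals in Section 12 and the synopsis is a separate matter. Each half-width is consistent with its own confidence level, and the difference adds nothing here.

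**Conclusion.** The point holds and should be fixed. The protocol's sole sample-size justification is stated from levels, and no precision is given for the change that is the primary endpoint. Under the assumptions of Step 3, 30 evaluable patients per arm give a 95% half-width for the change between about 0.21 and 0.61 against 0.35 stated, and a 90% half-width between about 0.17 and 0.51 against 0.285. The planned difference in medians is 0.84 − 0.58 = 0.26, so a range of this size affects what a reader may expect of the trial.

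The direction is unknown, since it turns on a correlation and a baseline spread that the protocol does not give. The finding does not show that 64 patients are too few, and it does not touch the validity of the randomised comparison. Confidence is high that the mismatch exists; the size of its effect is illustrative only.

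**What to change.** In Sections 1.1 and 12:

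- Restate the expected half-width for the 12-hour value minus the value at randomisation. Use paired data if available; otherwise give it over a stated range of correlations and baseline spreads.
- Name that difference as the variable whose location shift is estimated.
- State which time point the planning levels refer to.

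The endpoint, the non-parametric method and n=64 stay as they are.

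The cost is some wording and one recalculation, with no new data, visits or patients. The drawback is that without paired data the restated precision is a range and not one figure, and it may look less favourable than 0.35 or 0.285.

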## 13 Documentation, Data Management, Archiving

### 13.1 Patient Identification List

All subject data will be collected in a pseudonymized form. Every trial subject can be identified by a unique subject identification code. A confidential subject identification list which links the patients' names with the subject identification code will be stored in the investigator site file.

### 13.2 Source Data / Source documents

Source data are, within the meaning of the ICH E6 Guideline, all information in original records and certified copies of original records of clinical findings, observations, or other activities in a clinical trial necessary for the reconstruction and evaluation of the trial. Source data will be documented in various source documents (e.g. hospital records, doctor's report, subjects' diaries or evaluation checklists, x-rays) and then entered into the electronic Case Report Form (eCRF).

The following study specific data will be recorded directly in the eCRF and therefore will be considered as source data:

- KDIGO-criteria
- [TIMP-2]\*[IGFBP7]

The following study specific data will only be recorded electronically in separate files and is not going to be entered in the eCRF

- Biomarkers for add-on study (e.g. KIM-1, chitinase, NGAL, hyaluronic acid) and anti- and pro-inflammatory mediators (IL-6, IL-10...), leukocyte function

### 13.3 Recording of Data / Case Report Form (CRF)

Data will be recorded electronically using an EDC (Electronic Data Capture) system. Only persons authorized to enter data into the eCRF will have access to the EDC system. All users will be trained to use the EDC system and will comply with the instructions in the study-specific user manual. They will have continuous access to the data and reports of subjects at their own study site. The investigator is responsible for ensuring that the study data will be documented correctly, completely and in a timely manner. A study team physician takes on responsibility for the collected data by signing electronically. The electronic signature according to FDA 21 CFR Part 11 is the legally binding equivalent of the study team physician's handwritten signature.

### 13.4 Data Management

For data management, the validated data management system MACRO™ v4 (Elsevier Limited) will be used. All entered data will be stored on servers of the University Hospital Muenster. The servers are located in a secure data center and behind a firewall in the network of the University Hospital Muenster. A backup of the data will be saved on a daily basis and all data changes will be recorded in an audit trail.

All data will be checked for plausibility during initial data entry. Missing or non-plausible data are highlighted by the system right at input at the clinical study site and may be corrected immediately. Thereafter, according to the data validation plan, further data checks will be performed with regard to completeness and plausibility by the data management of the ZKS Muenster. In case of non-plausible or missing data, queries will be sent to the study site. The queries must be resolved by authorized members of the investigator's staff in the respective study site in a timely manner.

After completion of data entry and data processing, the database will be locked and the data will be exported for statistical analysis. The investigator will receive a CD-ROM of the eCRF data for archiving at the clinical study site.

## **13.5 Archiving**

After the end of the trial, the originals of all trial-specific documents (Trial Master File) including originals of the CRFs must be stored by the sponsor according to national regulations. Furthermore, the investigator stores the ISF (Investigator Site File) including copies of the CRFs for the time period given above.

No trial data or documents must be destroyed without prior written agreement between the sponsor and the investigator(s) or his/her designee.

## **13.6 Investigator Site File**

The Investigator Site File (ISF) will be checked regularly for completeness and actuality during monitoring. After the clinical trial is finished or stopped, the ISF has to be stored according to national regulations.

# **14 Monitoring, Audits and Inspections**

## **14.1 Monitoring**

In order to ensure a high degree of data quality, the study site will be monitored during the recruitment and follow-up period (frequency depending on the site's recruitment).

The objectives of the monitoring procedures are to ensure that the study safety and rights of the study subjects as a study participant are respected and that accurate, valid and complete data are collected, and that the study is conducted in accordance with the study protocol, the principles of GCP and local legislation.

The principal investigator agrees that the monitor will visit the study site in appropriate intervals. During these visits the monitor will check the quality of the data recording and ensure that the study site adheres to the timeframe as set in the study protocol. The investigators agree to provide any relevant information and documentation whenever the monitor requires this information. This includes access to all original study documents and source data.

It is the responsibility of the investigator to keep the participant's chart as complete as possible (e.g. history, concomitant diseases, inclusion in the clinical study, visit dates, results of laboratory tests, distribution of the study medication, and adverse events). Source data are checked and compared with entries in the eCRF. The participant has given consent with this procedure by signing the patient information and written informed consent form. Additional tasks of the monitor are:

- to check, whether the study site fulfils requirements of the clinical study (e.g. participant population, technical equipment),
- instruction of the investigators and personnel for the clinical study,
- to check the ISF for completeness and actuality,
- documentation of the status of the participant,
- matching of original data,
- to check SAE reports according to regulations.

The monitor has the responsibility to treat all information confidentially and to safeguard the integrity and personal privacy of the study participants.

The exact extent of the monitoring procedures is described in a separate monitoring manual.

## **14.2 Audits und Inspections**

For the purpose of ensuring compliance with the study protocol, the principles of GCP and local legislation, the sponsor may initiate an audit at any study site during the study and after completion. All study-related documentation must be made available to the designated auditor(s).

In addition, representatives of the regulatory authorities may choose to inspect the study site at any time prior to, during, or after completion of the clinical study. In this case, all pertinent study data should be made available as requested to the regulatory authority for verification, or inspection purposes. The investigator has to be available during these visits.

## **15 Ethical and Regulatory Requirements**

### **15.1 Declaration of Helsinki and Legal Requirements**

The study will be conducted in compliance with the declaration of Helsinki (current version, October 2013, Fortaleza), the requirements of the current German drug law ("Arzneimittelgesetz"), the current legal provisions regarding data protection, and the principles of Good Clinical Practice.

The present study will not be started before the ethics committee has given a favorable opinion and an approval by the responsible federal authority has been obtained.

In case of substantial amendments, a new application will be submitted to the ethics committee and/or the competent federal authority. Changes will not be implemented unless the competent ethics committee has given a favorable opinion and/or the competent authority has granted an approval.

Issues, which always require a favorable opinion of the ethics committee are for example:

- change of the investigator or his deputy,
- changes in any documents addressed to study participants or in any study information addressed to potential study participants.

According to German drug law §67, the investigator is required to notify the local surveillance authority about the beginning, the end and a premature termination of the study, about any substantial amendments and if the study is on hold. These notifications will be performed by a delegate of the sponsor (GCP-V, §12(3)).

Additionally, the investigator is required to notify the corresponding federal authority of the beginning of the study.

